11.2 Secondary Endpoints

11.2.1 *Time to death*

The time to death will be defined as the time from onset from symptoms until death from any cause. Patients who are alive or lost to follow-up at the cut-off date will be censored from this analysis.

11.2.2 *Mortality at 1 month*

1-month mortality is defined as the percentage of patients who have died 1 month from the time of start of treatment.

11.2.3 *Time to intubation*

The time to intubation will be defined as the time from symptom onset until time of intubation. Any patients already intubated at enrollment will be censored from this analysis.

11.2.4 *Time to improvement in oxygenation*

The time to improvement in gas exchange will be defined as the time from time of start of treatment until a $\geq 30\%$ decrease in oxygen requirement compared to

baseline [or elimination of oxygen requirement] without a decrease in SpO2 sustained for at least 48hrs or until discharge.

11.2.4 *Proportion of patients requiring ICU admission at 1 month.*

The proportion of patients requiring ICU admission will be calculated as the number of patients requiring ICU admission over the course of their hospitalization over the number of evaluable patients.

11.2.5 *Safety and Toxicity*

All subjects receiving at least one dose of the study drug will be evaluated for safety by monitoring symptoms, physical examinations, and laboratory tests. Adverse events will be classified and graded according to the NCI Common Toxicity Criteria version 5.0 (see Appendix A). The absolute number and frequency of each adverse event will be reported, and subdivided according to toxicity grade. A description of adverse events by treatment arm will also be reported. A particular adverse event occurring more than once in the same subject will be counted only once and at its worse grade.

11.2.6 *Duration of Hospitalization*

Duration of hospital admission will be measured from the time of admission until the time of discharge.

11.2.7 *7-point Ordinal Scale Score*

The mean/medians of the 7-point ordinal raw scores at day 14 from the start of treatment will be computed and compared between the treatment and control groups.

Exploratory Endpoints.

11.2.8 *Change in inflammatory markers from baseline*

Changes in LDH, D-Dimer, CRP, ESR, NLR and absolute lymphocytes before and after treatment and over time will be measured every other day during hospitalization.

11.2.9 *Change in circulating sIL-6 levels from baseline*

Change in sIL-6 levels before and after treatment and over time will be measured every other day during hospitalization.

11.2.10 *Radiographic response*

Radiological response will be evaluated by comparing % of lung fields with infiltrates on chest imaging (CXR and CT) through independent radiology review between baseline and day 8) if available.

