2. STUDY OBJECTIVES

Primary Objective

- To determine the **time to improvement in the 7-point ordinal scale** in patients treated with anti-IL-8 therapy compared to standard of care/controls.
 - Measured from baseline to 2 point or greater improvement in 7-point ordinal scale.

Secondary Objectives

- To evaluate the **time to death** in patients treated with anti-IL-8 therapy compared to controls.
- To evaluate the **mortality 1 month** after start of treatment in patients treated with anti-IL-8 therapy compared to controls.
- To determine the **time to intubation** in patients treated with anti-IL-8 therapy compared to controls.
 - Measured from time of disease onset to time of intubation.
- To estimate the **time to improvement in oxygenation** in patients treated with anti-IL-8 therapy compared to controls.
 - Measured as time from start of treatment until $\geq 30\%$ decrease in oxygen requirement compared to baseline
- To measure the **proportion of patients requiring ICU admission at 1 month** in patients treated with anti-IL-8 therapy compared to controls.
 - Measured as the number of patients requiring ICU admission over their hospitalization over the number of evaluable patients.
- To assess the **safety and tolerability** defined as adverse events graded by CTCAE v5.0 in patients treated with anti-IL-8 therapy compared to controls.
- To assess the **duration of hospitalization** in patients treated with anti-IL-8 therapy compared to controls.
 - Measured as time from admission to time of discharge.
- To compare the raw 7-point ordinal scale scores at day 14 in patients treated with anti-IL-8 therapy versus controls.

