5.1 Inclusion Criteria

- Male or female adult ≥ 18 years of age at time of enrollment.
- Confirmed diagnosis of SARS-CoV-2 infection ≤ 14 days prior to registration.

- Inpatient hospitalization (or documentation of a plan to admit to the hospital if the patient is in the emergency department)
- Evidence of pneumonia by chest radiographs, chest CT **OR** chest auscultation (rales, crackles).
- Severe respiratory disease (oxygen saturation $\leq 93\%$ on room air or requires $\geq 2\text{L}$ oxygen by NC in order to maintain $\text{SaO}_2 \geq 93\%$) **OR** critical respiratory disease (requiring non-rebreather, non-mechanical/mechanical ventilation, high-flow nasal cannula, ICU admission).
- Patients can continue their anti-cancer therapy at the discretion of the treating physician.
- *Adequate laboratory tests including:*
 - ANC $>500 \text{ cells/mm}^3$
 - Platelet count $>20,000 \text{ cells/mm}^3$
 - Serum total bilirubin $<1.5 \times \text{ULN}$
 - ALT $<5 \times \text{ULN}$
 - AST $<5 \times \text{ULN}$
- *Age and Reproductive Status*
 - a) Males and females, aged at least 18 years old
 - b) Women of childbearing potential (WOCBP) must have a negative serum or urine pregnancy test (minimum sensitivity 25 IU/L or equivalent units of human chorionic gonadotropin) within 24 hours prior to the start of study treatment.
 - c) Women must not be breastfeeding.
 - d) WOCBP must agree to follow instructions for method(s) of contraception for the duration of study treatment plus for a total of 155 days post treatment completion. Local laws and regulations may require use of alternative and/or additional contraception methods.
 - e) WOCBP who are continuously not heterosexually active are also exempt from contraceptive requirements, but should still undergo pregnancy testing as described in this section.
 - f) Males who are sexually active with WOCBP must agree to follow instructions for method(s) of contraception during study treatment with BMS-986253 for a total of 215 days post-treatment completion.
 - g) Azoospermic males are exempt from contraceptive requirements. WOCBP who are continuously not heterosexually active are also exempt from contraceptive requirements, and still must undergo pregnancy testing as described in this section.
- Willingness to provide written informed consent and HIPAA authorization for the release of personal health information, and the ability to comply with the study requirements

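### Time to death and time to intubation are counted from symptom onset with no delayed entry, so their Kaplan-Meier curves contain pre-randomization time in which no event could occur

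*Combined protocol and SAP*

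**What the plan says.** For time to death, section 11.2.1 reads: "The time to death will be defined as the time from onset from symptoms until death from any cause". For time to intubation, section 11.2.3 reads: "The time to intubation will be defined as the time from symptom onset until time of intubation". The intubation objective in section 2, repeated in the Protocol Synopsis, agrees: "Measured from time of disease onset to time of intubation".

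Section 11.2.2 puts the neighbouring mortality endpoint on another clock: "1-month mortality is defined as the percentage of patients who have died 1 month from the time of start of treatment". The primary endpoint (11.1.1) and time to improvement in oxygenation also begin at start of treatment.

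Eligibility (section 5.1) requires hospitalization or a documented plan to admit, with severe or critical disease. The critical category includes ventilated patients: "critical respiratory disease (requiring non-rebreather, non-mechanical/mechanical ventilation, high-flow nasal cannula, ICU admission". The only entry window is on diagnosis, "Confirmed diagnosis of SARS-CoV-2 infection ≤ 14 days prior to registration"; symptom duration has no limit.

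For patients already ventilated, section 11.2.3 adds: "Any patients already intubated at enrollment will be censored from this analysis". No censoring time is given.

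Section 13.2 applies Kaplan-Meier, log-rank and Cox methods to every time-to-event endpoint. Section 13 mentions neither delayed entry nor left truncation.

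**The concern.** Nobody who died between symptom onset and randomization can be in the trial. With an onset clock and no delayed entry, every enrolled patient is counted as at risk through an interval that enrolment guarantees was survived. The same holds for intubation among patients not yet intubated at entry.

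A reader will take a curve labelled time to death either as survival from onset or as survival after treatment, and on both readings it looks too favourable in both arms. The death curve at one month will also differ from the 1-month mortality reported beside it, because day 0 differs.

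A second, smaller problem concerns patients already intubated. On an onset clock their event has happened. If they are literally censored, they are counted as event-free up to the censoring time. If they are left out, they are not. The text does not settle which is meant.

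**Working it through.** **The plan's own figure.** The documents give no event count, power or expected rate for these two endpoints. The nearest stated figure is the 41 events for the primary endpoint (section 13.4). Schoenfeld's formula with HR 0.40, 2:1 allocation, one-sided 0.025 and 80% power gives (1.960 + 0.842)² / [(2/3)(1/3)(ln 0.40)²] = 42.07, or 43 rounded up, and 79.0% power at 41 events. That is close to the plan, and the time origin of the secondary endpoints does not enter it.

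**What the onset curve estimates.** Let L be the delay from onset to randomization and F(u) the probability of the event within u days of randomization. With complete follow-up to day t, the Kaplan-Meier estimate from onset equals the proportion of enrolled patients with the event by t days after onset, that is, the mean of F(t − L), with F = 0 for negative arguments.

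**Base case (assumed).** L is uniform on 3 to 14 days, the hazard is constant, and 25% have the event within 28 days of randomization. Then h = −ln(0.75)/28 = 0.010274 per day.
- Day 28, ordinary: 1 − [exp(−14h) − exp(−25h)]/(11h) = 18.1%. With delayed entry: 1 − exp(−25h) = 22.7%.
- Day 14, ordinary: 1 − [1 − exp(−11h)]/(11h) = 5.4%. With delayed entry: 1 − exp(−11h) = 10.7%.

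**Range.** F is Weibull with shape k, F(u) = 1 − exp[−(λu)^k], and λ = (−ln 0.75)^(1/k)/28, so that F(28) = 25% throughout. Entries are the ordinary onset curve at day 28 (numerical integration). The delayed-entry estimate (20,000 simulated patients per cell) is in brackets.

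| Delay, days (uniform) | Falling, k = 0.6 | Constant, k = 1 | Rising, k = 1.5 |
|---|---|---|---|
| 1-7 | 23.1% (32%) | 21.8% (24%) | 20.4% (21%) |
| 3-14 | 20.6% (33%) | 18.1% (23%) | 15.5% (17%) |
| 7-21 | 17.1% (33%) | 13.3% (20%) | 9.9% (13%) |

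The onset curve runs from about 10% to 23%, against 25% by 28 days after randomization in every cell. Its gap to delayed entry runs from about 1 to 16 points.

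**Person-time.** With 22.5% mortality by day 28 after randomization (midpoint of the 20-25% in section 3.1) and gamma delays with mean 5, 10 or 14 days, the death-free pre-randomization interval is 17%, 29% or 36% of all person-time.

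**Arm comparison.** Simulated log-rank tests for time to death used 92:46 patients, mean delays of 5 or 10 days, and 600 runs per scenario. One-sided type I error was 2.0-2.2% from onset and 2.2-2.8% from randomization. The simulation standard error is about √(0.025 × 0.975/600) = 0.6 points, so these do not differ meaningfully. Power was 38-39% on both clocks at HR 0.5, and 52-54% on both at HR 0.4.

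**Patients already intubated.** Assume 25% of the others are intubated within 28 days of randomization, a mean delay of 10 days, and 10-30% already intubated at entry. Cumulative intubation 28 days after onset is 16.1-16.7% if those patients are censored at enrolment, about 17% if they are excluded, and 25-42% if their earlier intubation is counted as an event. Censored at enrolment, they supply 3-11% of all person-time.

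**The case against.** The strongest reply is that the onset curve is not wrong for the cohort it describes. With complete follow-up it is exactly the proportion of enrolled patients who have had the event by that day after onset. This stands. The curve misleads when read as survival of patients from onset or after treatment, which are the readings its label invites.

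Second, the difference from delayed entry should not be called the bias. Delayed entry recovers an onset curve only if the hazard at a given time since onset is unrelated to when the patient entered. Under a hazard that falls after entry it gives 33% by day 28 from onset (3-14 day delay), when 20.6% of enrolled patients have had the event. So it is not a safe automatic substitute. Likewise, setting day 28 from onset beside day 28 from randomization shows a change of timescale, not an estimate of bias.

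Third, absolute mortality on a treatment clock is already available from 11.2.2, with exact intervals by arm. Section 13.2 promises medians only where possible, and at 20-25% mortality a median time to death may not be reached. Both points limit the harm.

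Fourth, a reader might infer that already-intubated patients certainly add event-free time. The documents do not support that as fact. Ordinary censoring is the meaning in 11.2.1 ("Patients who are alive or lost to follow-up at the cut-off date will be censored from this analysis"), but 11.2.13 uses the same term, for time on ventilation, of patients who were never intubated. They have no start time, so there it can only mean left out. Exclusion may be what 11.2.3 intends, and censoring or excluding these patients changes the curve by less than one point in the working above.

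**Conclusion.** The concern holds as a point about the descriptive estimates of two secondary endpoints. Following the plan as written puts guaranteed event-free time before randomization into both curves and into any medians, and sets time to death on a different clock from 1-month mortality. With 25% of events within 28 days of randomization, day 28 from onset would show about 10-23%. The documents give neither the onset-to-randomization delay nor the hazard shape, so that range is illustrative.

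A reader might go further and infer a bias between arms. The documents do not support this: randomization balances the delay in expectation, the test remains valid under the null, and the simulated error rate and power barely moved. The primary endpoint, its 41 events, the sample size of 138 and the 1-month mortality endpoint are untouched. The handling of already-intubated patients is an ambiguity to resolve, with literal censoring as the reading to rule out. The change should be made, but it is not critical to the trial's main conclusion.

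**What to change.** - In 11.2.1 and 11.2.3, measure time to death and time to intubation from randomization in both arms. Make the same change to the intubation objective in section 2 and in the Protocol Synopsis.
- Either give 1-month mortality (11.2.2) the randomization origin too, or state how start of treatment relates to randomization. Otherwise the two mortality endpoints still have different stated clocks.
- In 11.2.3, say that patients already intubated at randomization are excluded from the time-to-intubation analysis, in place of censored.
- If an onset-based curve is wanted, make it supplementary, with delayed entry at randomization and its assumption of independent entry stated.

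The cost is wording in these places. The randomization date is available for every patient, no new data are needed, and the sample size and primary analysis do not change.

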3. BACKGROUND

3.1 Disease Background

Coronavirus disease 2019 (COVID-19) represents an emerging public health crisis that is caused by infection with the novel coronavirus, severe acute respiratory syndrome coronavirus 2 (SARS-CoV-2), which is associated with high transmissibility and mortality.¹ The World Health Organization (WHO) has defined COVID-19 as a pandemic. Symptoms include fever, cough, myalgias, shortness of breath and are most commonly mild in severity. However approximately 14% of patients with COVID-19 will develop severe disease (defined as dyspnea, respiratory frequency ≥ 30 /minute, blood oxygen saturation $\leq 93\%$, PaO₂/FiO₂ ratio < 300 , and/or lung infiltrates $> 50\%$ of the lung field within 24-48 hours).² Although the overall mortality appears $< 1\%$, patients with severe disease have a mortality of approximately 20-25% across multiple studies reported to date.³⁻⁵ Medical co-morbidities also appear associated with particularly poor outcomes.³ Particular, in cancer patients, reports suggest a mortality as high as 7%. Cancer patients also appear to have a dramatically increased rate of severe events (invasive ventilation or

death), with a rate of 40% in a small study from China.⁶ Novel strategies to address respiratory failure in COVID patients generally and cancer patients in particular represents an urgent and critical need.

Figure 1 Clinical Course of Patients with COVID-19

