11.2.11 Proportion of patients with multiorgan failure at 1 month

The proportion of patients with multiorgan failure will be defined as the number of patients with multiorgan failure during their hospitalization measured at 1 month over the number of evaluable patients.

11.2.12 Time to improvement in NEWS2 score ≤ 2

Determine the time to improvement in NEWS score will be defined as time from start of treatment until NEWS score ≤ 2 and maintained for at least 24hrs. The NEWS 2 score is calculated based respiratory rate, oxygen saturation, systolic blood pressure, pulse rate, level of consciousness/confusion and temperature.

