13.2 Study Endpoints and Analysis Plan

All subjects who receive at least one dose of study drug will be considered evaluable and included in the efficacy and safety analysis.

Analytic plan for primary objective:

The primary efficacy null hypothesis of the equality of time to improvement (2 points) in clinical status curves will be tested with the log-rank test. The overall type I error for the primary analysis will be considered one-sided alpha of 0.025. Kaplan-Meier estimates will be reported for each of the two arms with median time to improvement and 95% confidence intervals (CI). Cox regression will be employed to estimate the treatment effect (HR) and 95% CI.

Analytic plan for secondary and exploratory objective:

We will estimate the distributions of all time-to-event endpoints using the Kaplan-Meier method and if possible, provide medians (95% CI). Comparisons between survival curves will be assessed using log-rank tests and Cox regression models.

For each arm, we will estimate the 1-month mortality rate and incidence of adverse events graded by CTCAE v5.0 using the exact 95% confidence intervals. Comparisons between the two arms will be assessed using chi-squared or Fisher's exact tests. The mean/medians of the 7-point ordinal scores at day 14 after the start of treatment will be computed and compared between the two groups using two-sample t-test or the equivalent non-parametric Wilcoxon Rank-Sum test if normality is not satisfied.

Changes in exploratory endpoints (before and after treatment) will be quantified using means (95% CI) and/or medians (inter-quartile ranges) for non-normal data. Comparisons between the two arms will be made using two-sample independent t-tests or the non-parametric equivalent, Wilcoxon Rank-Sum test. The associations between baseline levels and/or changes over time of IL-8 and other key cytokines (TNF, IL-1b, IL-6) with outcomes will be assessed using regression models.

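### Deaths without intubation or ICU transfer are not accounted for in the time-to-intubation, ICU-admission and multi-organ-failure results; a competing-risk estimate and event-or-death counts are needed beside them

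*Combined protocol and SAP*

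**What the plan says.** All references are to the combined protocol and SAP.

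- **Time to intubation (11.2.3, secondary).** "The time to intubation will be defined as the time from symptom onset until time of intubation". The only censoring rule given is "Any patients already intubated at enrollment will be censored from this analysis". Death before intubation is not mentioned.
- **ICU admission (the second section numbered 11.2.4, secondary).** The measure is the "number of patients requiring ICU admission over the course of their hospitalization over the number of evaluable patients".
- **Multi-organ failure (11.2.11, exploratory).** The measure has the same form: "the number of patients with multiorgan failure during their hospitalization measured at 1 month over the number of evaluable patients".
- **Denominator (13.2).** "All subjects who receive at least one dose of study drug will be considered evaluable and included in the efficacy and safety analysis". Nothing in this removes a patient who dies early or counts that patient as a failure.
- **Methods (13.2).** "We will estimate the distributions of all time-to-event endpoints using the Kaplan-Meier method and if possible, provide medians (95% CI"; then "Comparisons between survival curves will be assessed using log-rank tests and Cox regression models". No competing-risk method or composite is named.
- **Expected mortality (3.1).** "patients with severe disease have a mortality of approximately 20-25% across multiple studies reported to date". It is not split by intubation or ICU status.
- **Where death does count.** Time to death (11.2.1) and 1-month mortality (11.2.2) are separate secondary endpoints. The ordinal score compared at day 14 (11.2.7) gives death 1 and invasive ventilation 2.

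**The concern.** Each of the three endpoints records a failure that death can prevent. A patient who dies on the ward can no longer be intubated, moved to ICU or develop organ failure.

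The consequence differs by type of endpoint. In a Kaplan-Meier analysis that censors the death, the patient leaves the risk set as though intubation could still have happened later. The curve then estimates intubation in a setting without death, which is higher than the share of patients actually intubated. In the two proportions, the patient stays in the denominator and never enters the numerator, so a ward death and a recovery are scored alike.

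What is at stake is the reading of supportive evidence. If the arms differ in deaths on the ward, these endpoints can stay flat or move against the drug while survival improves. A reader who takes them one at a time would miss that. Leaving the handling of death unstated in an open-label trial also leaves the choice open until the data are known.

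**Working it through.** The plan gives no event rate, sample size or power for these endpoints, so there is no figure of its own to reproduce. The 41 events in 13.4 belong to the primary endpoint and play no part here.

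**How many patients could be affected.** Mortality of 20-25% is from 3.1. The share of deaths that occur without intubation is not in the documents; I assume 10% to 50%.

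- Low end: 0.10 × 20% = 2% of patients, about 3 of 138.
- High end: 0.50 × 25% = 12.5% of patients, about 17 of 138.

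**Kaplan-Meier with death censored.** Assume constant cause-specific hazards over 28 days. Let I be the true cumulative incidence of intubation and D that of death without intubation. The total cumulative hazard is H = −ln(1 − I − D). The intubation part is Λ = H × I/(I + D). Censoring deaths gives 1 − KM = 1 − exp(−Λ). The rates below are assumed.

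| Scenario | I | D | H | Λ | 1 − KM | Excess over I | Intubation or death |
|---|---|---|---|---|---|---|---|
| A: control | 20% | 8% | 0.3285 | 0.2346 | 20.9% | 0.9 points | 28% |
| B: ward deaths halved, none intubated | 20% | 4% | 0.2744 | 0.2287 | 20.4% | 0.4 points | 24% |
| C: ward deaths halved, rescued patients intubated | 24% | 4% | 0.3285 | 0.2816 | 24.5% | 0.5 points | 28% |

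- B against A: the cause-specific HR is 0.2287/0.2346 = 0.97. The endpoint barely moves, while intubation-or-death falls from 28% to 24%.
- C against A: the cause-specific HR is 0.2816/0.2346 = 1.20. Intubation really does rise, and intubation-or-death is equal.

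**Simulated HRs under other assumed rates.** Take 30% of controls intubated by day 28; 5%, 10% or 15% of controls dying on the ward; half of those deaths averted by the drug; and a share q of averted deaths intubated 3 days later. Allocation is 2:1. HRs are for 5% / 10% / 15% ward deaths.

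| q | HR, death censored | HR, intubation or death |
|---|---|---|
| 0 | 0.99 / 0.97 / 0.96 | 0.91 / 0.85 / 0.80 |
| 0.5 | 1.03 / 1.05 / 1.08 | 0.96 / 0.91 / 0.88 |
| 1 | 1.07 / 1.14 / 1.22 | 0.99 / 0.98 / 0.98 |

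**ICU proportion, same assumptions, 30% in control.** The treated proportion is 30% + q × D/2, ignoring the 3-day delay.

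- q = 0: 30% for every D, so no change.
- q = 0.5: 31.25%, 32.5% and 33.75%.
- q = 1: 32.5%, 35% and 37.5%.

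The proportion never falls when deaths are averted. It rises only when q is above zero.

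**The case against.** **Censoring at death is inferred.** No sentence says that un-intubated deaths are censored. This stands. For time to intubation the gap is silence plus the default behaviour of the named methods. For the two proportions the result follows directly from the definitions.

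**A reader might infer that time to intubation scores a ward death as highly as a recovery.** It does not. A censored patient leaves the risk set, whereas a recovered patient stays in it. Log-rank and Cox with death censored are a valid comparison of cause-specific hazards. The equal scoring applies only to the ICU and multi-organ-failure proportions.

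**A reader might infer that the trial gives no credit for averted deaths.** The documents do not support that. Time to death, 1-month mortality and the day-14 ordinal score all register them. The limitation is confined to these three endpoints.

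**Apparent harm can be an accurate result.** In scenario C intubation truly rises from 20% to 24%, and an endpoint with that name should show it.

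**Composites do not settle the matter.** In scenario C the composite is 28% in both arms and also hides the halving of ward deaths. This stands, and it is why composites should sit beside the existing endpoints with their components shown.

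**The stakes are limited.** None of these endpoints is primary or drives the sample size or the interim analysis. With 92 and 46 patients, the standard error of a difference near 20% is √(0.2 × 0.8 × (1/92 + 1/46)) = 7.2 points, so the 3.6-point gap between C and A is about half a standard error.

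**Conclusion.** The point holds within limits. Under the methods in 13.2, deaths without intubation would by default be censored, and 1 − KM would overstate the incidence of intubation by about 0.4 to 0.9 points in the scenarios above. The ICU-admission and multi-organ-failure proportions count a death without the event as a non-event. With mortality of 20-25% cited, none of the three results can be interpreted without mortality beside it.

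The stronger reading, that a life-saving drug would look harmful on these endpoints, is not supported in general. It requires that some averted deaths are later intubated or admitted to ICU. If none are, the intubation HR stays at 0.96 to 0.99 and the ICU proportion is unchanged. If half or all are, the HR is 1.03 to 1.22.

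All of these sizes rest on assumed intubation and ward-death rates. The documents give only overall mortality in severe disease. The definitions themselves rest on no assumption.

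**What to change.** 1. **Time to intubation.** In patients not intubated at randomization, replace the Kaplan-Meier estimate with the cumulative incidence of intubation, treating death as a competing event. Keep log-rank and Cox, labelled as cause-specific comparisons, and state that deaths are censored in them.
2. **Added summaries beside the existing endpoints, by day 28.** Report intubation or death (patients not intubated at randomization), ICU admission or death (patients not in ICU at randomization), and multi-organ failure or death. Give component counts by arm for each. The ICU restriction is needed because 5.1 admits patients already in ICU, who would otherwise have the event at entry.
3. **Reporting.** Present these results together with mortality.

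The cost is a few sentences of analysis text and no extra patients. The daily ordinal score captures invasive ventilation, and survival is already followed. The study calendar in section 10 lists no ICU or organ-failure item, so the sponsor should confirm that the case report form records both, with ICU status at randomization. The drawback is that composites mix events of different severity, which is why the components must be shown. The symptom-onset time origin is a separate matter that this change does not address.
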